1 SYNOPSIS

Title

Stereotactic Laser Ablation for Temporal Lobe Epilepsy (SLATE)

Protocol Number: CS-05000 IDE Number: G150255

Purpose

The purpose of this study is to evaluate the safety and efficacy of the Visualase® MRI-Guided Laser Ablation System (Visualase System).

Design

Prospective, single-arm, multicenter study

Medical Device

The Visualase System comprises four components: a laser energy source, a cooled laser applicator, a circulating pump for circulating coolant through the applicator, and a computer workstation with magnetic resonance imaging (MRI) analysis software for determination and visualization of relative changes in tissue temperature during surgical ablation.

All devices used in this study are FDA cleared and commercially released. Devices become investigational only when accessed or opened with the intent to be used within the context of the study.

Objective and Endpoints

Objective: To evaluate the safety and efficacy of the Visualase System for necrotization or coagulation of epileptogenic foci in patients with intractable mesial temporal lobe epilepsy (MTLE)

Primary Safety Endpoint

Incidence of qualifying device-, procedure-, or anesthesia-related adverse events (AEs) (defined in Appendix F) through 12 months following the Visualase procedure

Primary Efficacy Endpoint

Seizure freedom (defined as Engel Class I, Appendix C) at 12 months following the Visualase procedure

Secondary Endpoints

- Seizure freedom (defined as Engel Class I, Appendix C) at 12 months following the Visualase procedure compared to historical control for continued medical therapy
- 2. Seizure freedom (defined as Engel Class I, Appendix C) at 12 months following the Visualase procedure, including subjects who are retreated with Visualase
- 3. Within-subject change of Boston Naming Test score (English language version), from baseline to 12 months following the Visualase procedure
- 4. Within-subject change of Rey Auditory Verbal Learning Test 5-Trial Total score (English language version), from baseline to 12 months following the Visualase procedure

- 5. Within-subject change of Quality of Life in Epilepsy Inventory (QOLIE-31) score (English language version), from baseline to 12 months following the Visualase procedure
- 6. Within-subject change of SF-36 quality of life questionnaire Mental Component Score (English language version), from baseline to 12 months following the Visualase procedure
- 7. Within-subject change of SF-36 quality of life questionnaire Physical Component Score (English language version), from baseline to 12 months following the Visualase procedure
- 8. Seizure freedom (defined as Engel Class I, Appendix C) at 12 months following the Visualase procedure compared to historical control for open surgical resection

Subject Population

The study subject population is adult patients with medically intractable (per the definition by the International League Against Epilepsy¹) mesial temporal lobe epilepsy

(MTLE), with radiological and electrophysiological evidence consistent with unilateral focal seizure onsets.

A minimum of 150 subjects will undergo the Visualase procedure and be evaluated at up to 25 sites in the United States. To account for attrition, up to 215 subjects may be enrolled.

The duration of subject participation from enrollment through study exit is expected to be approximately 13 months.

Treatment

Following informed consent, subjects' qualification for the Visualase procedure will be confirmed by a central review committee. Baseline assessments will also be performed at any time prior to the Visualase procedure.

Subjects will then undergo MRI-guided laser ablation of the amygdala and hippocampus with the Visualase System. Subjects will be followed for 12 months following the Visualase procedure and assessed for adverse events, seizures, neuropsychological outcomes, mood, and quality of life outcomes. Figure 1 below illustrates the study design. Refer to Table 2 for required study visits and required assessments/procedures during each visit.

[figure not shown]

Figure 1: Study Design

Inclusion Criteria

- 1. Adult subjects ≥ 18 years of age and ≤ 70 years of age at the time of enrollment
- 2. History of medically refractory (or intractable) MTLE, defined per the International League Against Epilepsy (ILAE)¹ as: failure of adequate trials of two tolerated and appropriately chosen and used antiepileptic drug (AED) schedules (whether as monotherapies or in combination) to achieve sustained seizure freedom, as determined by the Investigator
- If the subject has a vagus nerve stimulator (VNS), the subject must have failed to achieve sustained seizure freedom with the VNS implanted for at least 6 months prior to enrollment
- 4. On stable antiepileptic drugs (AEDs) (and/or stable VNS setting, if applicable) for 30 days prior to the procedure and compliant with medication use, as reported by the subject

- 5. An average of at least 1 complex partial or secondarily generalized seizure compatible with MTLE per month, for a minimum of the last 12 months prior to enrollment (i.e., at least 12 qualifying seizures in the 12 months prior to enrollment)
- 6. Subject's seizure symptoms and/or auras are compatible with MTLE
- 7. Based on video EEG obtained within 24 months of enrollment, evidence of seizures from one temporal lobe consistent with MTLE. If the video EEG was obtained more than 12 months prior to enrollment, an interictal EEG done within 12 months of enrollment must show interictal spikes in the same distribution as seen in the previous video EEG monitoring.
- 8. Based on MRI obtained within 24 months prior to enrollment, evidence consistent with mesial temporal lobe sclerosis (defined as: mesial temporal atrophy accompanied by either increased signal on T2-weighted image, indicative of gliosis, or accompanied by loss of internal architecture in the hippocampus). If there is evidence of a change in clinical seizure symptoms/severity or of a brain injury since the MRI, a repeat MRI must be obtained to confirm eligibility.
- Subject is willing and able to remain on stable AEDs (and stable VNS setting, if applicable), as directed by their treating physician, for 12 months following the Visualase procedure
- 10. Subject is able to complete study assessments in English or Spanish language
- 11. According to Investigator judgment, subject is willing and able to comply with protocol requirements (e.g., follow-up visit schedule, evaluations, compliance with AED regimen)

Exclusion Criteria

- 1. Subject is unwilling or unable to sign the study informed consent form (ICF)
- 2. Subject is pregnant prior to the Visualase procedure or intends to become pregnant during the course of the study
- 3. Subject is currently implanted with a device contraindicating MRI, including deep brain stimulation or responsive neurostimulator
- 4. Subject has progressive brain lesions and/or tumors not associated with epileptic disease state
- 5. Subject has a history of previous intracranial surgery for treatment of epileptic seizures, including intracranial resections, stereotactic radiosurgery, or deep brain stimulation
- 6. Subject has persistent (based on medical judgment) extra-temporal or predominant contralateral focal interictal spikes or slowing, or generalized interictal spikes on EEG
- 7. Subject has seizures with contralateral or extra-temporal ictal onset on EEG
- 8. Subject's aura and/or ictal behavior suggest an extra-temporal focus

- 9. Subject has evidence on MRI of epileptogenic extra-temporal lesions, dual pathology within the temporal lobe, or contralateral hippocampal increased T2 signal changes and/or loss of internal architecture
- 10. If additional testing (e.g., PET, SPECT, invasive EEG or MEG) has been performed, results are discordant with the seizure focus scheduled for ablation
- 11. As reported by the subject or in the opinion of the Investigator, the subject is not compliant with AED medication requirements
- 12. Subject has an IQ < 70, based on the Wechsler Abbreviated Scale of Intelligence (WASI or WASI-II) or Wechsler Adult Intelligence Scale Full Scale IQ or General Ability Index (WAIS-III or WAIS-IV FSIQ or GAI) performed within 12 months prior to enrollment, or after enrollment but prior to the procedure
- 13. Subject has been diagnosed with dementia or other progressive neurological disease
- 14. Subject has an unstable major psychiatric illness, psychogenic non-epileptic seizures, or medical illness that would contraindicate the Visualase procedure or affect the neuropsychological assessments
- 15. Subject is currently participating in other research that may potentially interfere with SLATE endpoint(s), as determined by the Investigator or Sponsor
- 16. Subject is allergic to gadolinium

Clinical Procedures

Subjects will be considered enrolled upon signing and dating the ICF and will be exited from the study upon completion of Follow-up Visit 4 twelve months following the Visualase procedure, or upon withdrawal. Required study visits and procedures are outlined in the Schedule of Events (Table 2) below.

Table 2. Schedule of Events

Table 2. Schedule of Events									
Assessment/Procedure	Enrollment / Screening	Baseline	Visualase Procedure	Follow-up Visit 1 14 days (±7days)	Follow-up Visit 2 3 mos (90±14 days)	Follow-up Visit 3 6 mos (180±30 days)	Follow-up Visit 4 12 mos (365+45 days)	Unscheduled Visit	
Informed consent	Х								
Demographics	Χ								
Medical/surgical history (including MRI & video EEG)	X ¹								
Epilepsy/seizure history	Χ								
AED & psychotropic medications recorded ²	х	Х	Х	Х	Х	Х	Х	X ³	
Pregnancy test	Х		X ⁴						
IQ test ⁵	X ⁶								
Neurological exam, including oculomotor nerves & confrontation visual field test for AE reporting		Х		х	Х	Х	х		
Adverse event assessment	Χ	Χ	Х	Х	Χ	Х	Х	Χ	
Healthcare services utilization assessment			Χ	х	Х	х	Х	Χ	
Boston Naming Test		X ⁶				Х	Х		
COWA (FAS)		X ⁶				Х	Х		
Emory Semantic Fluency Tasks		X ⁶				Х	Х		
Emory Famous Faces Naming/Recognition		X ⁶				Х	Х		
Rey Auditory Verbal Learning Test		X ^{6,7}				X8	X ⁷		
WMS-IV Visual Reproduction Test		X ⁶				Х	Х		
WMS-IV Verbal Paired Associates		X ⁶					Х		
Beck Depression Inventory-II ⁹		Χ				Х	Х		
Beck Anxiety Inventory ⁹		Χ				X	Х		
QOLIE-31 ⁹		Χ				Х	Х		
SF-36 ⁹		Χ				Х	Х		
Seizure Severity Questionnaire Version 39		Χ				X ¹⁰	X ¹⁰		
Seizure diary review ¹¹	Х	X ³	X^3	Х	Χ	Х	X	X^3	
Seizure classification ¹³	Х	X ³	X^3	Х	Χ	Х	Х	X^3	
Research MRI		Χ				Х			
Visualase procedure (including pre & post ablation MRI scans)			Χ						
Pain NRS			X ¹²						
Assessment of driving and employment/school status		Х					Х		
Neuro-ophthalmologic exam of acuity, fields and extraocular movements ¹⁴		X ⁶			Х	X ¹⁵	X ¹⁵	X ¹⁶	

AED=Antiepileptic drugs; COWA (FAS)=Controlled Oral Word Association Test; EEG= electroencephalogram; QOLIE-31=Quality of Life in Epilepsy Inventory; WAIS=Wechsler Adult Intelligence Scale; WASI=Wechsler Abbreviated Scale of Intelligence; WMS-IV=Wechsler Memory Scale

¹Includes past AEDs, MRI, and video EEG (and Wada test, functional MRI, MEG, PET and/or SPECT scan if available)

²AEDs and their dosages should remain stable from 30 days prior to the procedure through the 12 month post procedure visit.

³Assessments should be done if possible.

⁴To be performed within 7 days prior to the Visualase procedure for all females of childbearing potential ⁵WAIS-III or WAIS-IV (FSIQ or GAI), or WASI or WASI-II are acceptable for screening. If scores are not available in the medical record, one of these assessments will be administered post-consent.

⁶Results of assessments performed within 12 months prior to enrollment may be used.

⁷Administer Form A.

8Administer Form GE-AB.

⁹Self-reported by subjects.

¹⁰The Seizure Severity Questionnaire is completed only by subjects who have had seizures within the 4 weeks preceding the 6- and/or 12-month visits.

¹¹.The seizure diary will be provided to the subject after consent, prior to submission to the Pre-Surgical Evaluation Committee. Subsequent reviews shall occur at indicated timepoints. Reviews at the Baseline Visit, Visualase Procedure and Unscheduled Visits are encouraged, though not required.

¹²The pain scale is to be completed following the Visualase procedure but prior to discharge.

¹³Seizure classification will initially be conducted after consent, prior to submission to the Pre-Surgical Evaluation Committee, and then amended throughout the subject's participation in the study if new seizure types occur.

¹⁴Subjects who were enrolled and received treatment under a CIP version prior to 4.0 should be reconsented to have a neuro-ophthalmologic exam at their next scheduled study visit.

¹⁵Any subject consenting to CIP 4.0 who has an abnormal neuro-ophthalmologic finding at any follow-up visit is required to have neuro-ophthalmologic exams at subsequent study follow-up visits until the finding is resolved or until Follow-up Visit 4, whichever occurs first.

¹⁶If a subject consented to CIP 4.0 has symptoms of a potential vision-related adverse event prior to the 3-month follow-up visit, a neuro-ophthalmologic exam will be performed for evaluation.

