7.8 Data Collection

Data will be collected using an electronic data capture system. CRF Instructions will include details regarding appropriately completing eCRFs and allowable data on eCRFs. Data collection requirements at each visit are summarized in Table 4 below.

Table 4: Data Collected at Subject Visits

Table 4: Data Collected at Subject visits									
Case Report Forms	Enrollment / Screening	Baseline	Visualase Procedure	Follow-Up Visit 1 (14 day)	Follow-Up Visit 2 (3 mo)	Follow-Up Visit 3 (6 mo)	Follow-Up Visit 4 (12 mo)	Unscheduled Visit	
Site Data Collection									
Informed Consent, Demographics	Х								
Seizure Classification Form	Χ	X^1	X ¹	X ¹	X ¹	X ¹	X ¹	X ¹	
Epilepsy History	Х								
Surgical Plan	Х								
Medical History	Х								
Medications	Х	X ¹	X ¹	X ¹	X ¹	X ¹	X ¹	X ¹	
VNS Setting	X ¹	X ¹	X ¹	X ¹	X ¹	X ¹	X ¹	X ¹	
Eligibility Criteria, Pregnancy Test	Х		X ¹						
EEG and Additional Testing	Χ								
MRI	Х	Х	Х			Х			
Pre-Surgical Evaluation Submission	Х								
Neurological Exam		Χ		Х	Χ	Χ	Х		
Neuro-ophthalmologic Exam		X ⁴			X ⁴	X ⁴	X ⁴	X ⁴	
Neuropsych + QOL		Х				Х	Х		
Seizure Diary Summary, Seizure Log		X ¹	X ¹	Х	Х	Х	Х		
Visualase Procedure, Product Disposition			Х						
Procedure Steroid Log			X ¹						
Study Visit ²		X^2		Х	Х	Χ	X ²		
NRS Pain Scale			X ³						
Retreatment Submission								X ¹	
Secondary Procedure								X ¹	
Healthcare Services Utilization			Х	X ¹	X ¹	X ¹	X ¹	X ¹	
Study Exit		X ¹	X ¹	X ¹	X ¹	X ¹	Х	X ¹	
Adverse Event	X ¹	X ¹	X ¹	X ¹	X ¹	X ¹	X ¹	X ¹	
Device Deficiency			X ¹						
Protocol Deviation	X ¹	X ¹	X ¹	X ¹	X ¹	X ¹	X ¹		

Case Report Forms	Enrollment / Screening	Baseline	Visualase Procedure	Follow-Up Visit 1 (14 day)		F _C	Follow-Up Visit 4 (12 mo)	Unscheduled Visit
Commit	ttee/Cor	e Lab	Evaluati	on Data	Collect	tion		
Pre-Surgical Evaluation	Х							
Retreatment Evaluation								X ¹
Volumetric Analysis						Х		
Neuropsych + QOL Analysis		Х				Х	Х	
Neuro-ophthalmologic Analysis		X ⁴			X ⁴	X ⁴	X ⁴	X ⁴

¹If applicable, events, changes or updates should be captured on eCRFs as they occur.

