7.19 Study Exit

A study exit eCRF is required for all subjects. Prior to exiting a subject from the study, it is recommended to follow the subject until all ongoing device-related, anesthesia-related, and/or procedure-related AEs are resolved or unresolved with no further actions planned. Upon exiting from the study, no further study data will be collected and no further study visits will occur for the subject. All data available through the time of the subject's exit will be used for analysis.

Subjects are urged to remain in the study as long as possible but may be exited from the study for any of the following situations:

- Subject has completed follow-up
- Subject lost to follow-up

- Subject death
- Subject did not meet inclusion/exclusion criteria (If ineligibility is discovered after the Visualase procedure, the subject will still be followed through 12 months post procedure.)
- Subject chooses to withdraw (e.g., consent withdrawal, relocation to another geographic location)
- Investigator deems withdrawal necessary (e.g., the subject enrolls in a confounding investigational study, the subject fails to maintain adequate study compliance, or it is medically necessary or in the best interest of the subject)

The following information is required to be documented at study exit:

- Reason for exit
- Date of study exit
- If the subject is determined to be lost to follow-up, details of a minimum of 3 contact attempts via 2 different methods (e.g., email, phone, and/or certified letter) must be recorded.

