14 STATISTICAL METHODS AND DATA ANALYSIS

14.1 Sample Size Determination

Subjects will be considered enrolled upon the signing of a consent form. It is anticipated that once enrolled, some subjects will not proceed to the Visualase procedure due to failure at their pre-surgical evaluation, changes in clinical status, or non-compliance to protocol. Based on these factors, and on previous reports of attrition in similar studies, the assumed attrition rate is 30%. To account for this attrition, up to 215 subjects may be enrolled to ensure at least 150 subjects are treated with the Visualase procedure.

The primary efficacy endpoint is the 12-month seizure-free rate. The analysis of the primary efficacy endpoint will include a point estimate and exact 95% confidence interval (CI) of the rate. The lower bound of the 95% CI of the seizure freedom rate following the Visualase procedure must be above 43%. Based on published and unpublished accounts of seizure freedom rates following laser ablation for MTLE, it is expected that approximately 56% of subjects who undergo the Visualase procedure will be seizure free through 12 months post procedure. Given these assumptions, 89% power can be achieved with data from 150 treated subjects.

Certain secondary endpoint assessments will be made using subject questionnaires. These self-reported instruments are influenced by primary language. Validated translations are not available in all languages, thus enrollment will be limited to subjects who can complete these assessments in either English or Spanish. Further, the impact of grouping across translations for analysis is an important consideration. Therefore, for the specified secondary cognitive and QOL endpoints, the subset of only the Englishlanguage versions will be used for analysis. To preserve adequate statistical power for analysis of this subset, the total Spanish language enrollment will be restricted to no more than 40% of the total study-wide enrollment population.

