14.2 General Considerations

Statistical analyses will be performed using SAS Software, Version 9.4 or later.

All statistical tests will be conducted at a two-sided alpha level of 0.05 unless otherwise stated.

A Statistical Analysis Plan (SAP) will include a comprehensive description of the statistical methods and reports to be included in the final study report. Any change to the analysis methods described in the protocol will require an amendment only if it changes a principal feature of the protocol. Any other change to the analysis methods described in the protocol, and the justification for making the change, will be described in the clinical study report.

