7.1.3.2 Modified Intent to Treat (mITT) Population

All subjects who enter the operating room and start the Visualase procedure (i.e., undergo scalp incision) will be included in the mITT analysis population. The mITT population will be the primary analysis population for efficacy evaluations.

Non-compliance is defined as any subjects who have not submitted enough seizure diaries or qualifiers in their seizure diaries through 12 months, from which the Engel I Classification could not be determined at study exit because of the missing information. The detail of the seizure diaries refers to section 7.5.1 of CIP.

SLATE Statistical Analysis Plan Revision 1.0 Page 9 of 23 Medtronic

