7.4 Handling of Missing, Unused, and Spurious Data and Dropouts

7.4.1 Missing Data

Missing primary efficacy endpoint values and missing secondary endpoint values associated with testable hypotheses will be imputed for analysis with the mITT analysis population. Missing primary efficacy endpoint data will be imputed as a binary outcome of seizure freedom, regardless of missing pattern. No daily level imputation will be conducted.

The primary method of imputation will be multiple imputation (SAS PROC MI followed by MIANALIZE). Ten repetitions will be performed and, if needed, will be increased until the algorithm converges.

The Markov chain Monte Carlo (MCMC) method or Fully Conditional Specification (FCS) will be used with the default number of burn-in iterations before the imputation. The model variables will include: age, sex, race (white, African American, or other), and duration of disease.

SLATE Statistical Analysis Plan		Form
Revision 1.0	Page 10 of 23	Medtronic

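### Seizure status is not a required item at early exit, so a primary outcome already settled in a subject's diary may go uncollected and be imputed

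*Protocol*

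**What the plan says.** **Collection.** Under Protocol 7.5.1 subjects keep a paper diary until study exit, but sites review and collect it at specified visits. For the remaining occasions, Table 2 footnote 11 states: "Reviews at the Baseline Visit, Visualase Procedure and Unscheduled Visits are encouraged, though not required". Protocol 7.16 makes adverse event and healthcare utilization assessment mandatory at an unscheduled visit and lists diary review among items to be done as possible or necessary. Table 2 lists diary review in the unscheduled column. Table 4 (Protocol 7.8) has a row for "Seizure Diary Summary, Seizure Log" with no mark in that column, although it allows the Study Exit form there.

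**Exit.** Protocol 7.19 introduces its list with "The following information is required to be documented at study exit". The items are reason, date and, for a subject lost to follow-up, details of contact attempts. Diary return and seizure status are not listed, no early-exit visit is described, and no data are collected after exit.

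**Analysis.** SAP 7.1.3.2 foresees subjects for whom "the Engel I Classification could not be determined at study exit because of the missing information". SAP 7.4.1 states: "Missing primary efficacy endpoint data will be imputed as a binary outcome of seizure freedom, regardless of missing pattern". The model variables it names are age, sex, race and duration of disease. The one visible exception, in SAP 7.4.3, is a seizure-related death.

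**The concern.** The endpoint window runs from day 30 to day 365. Class I-C needs two years free of disabling seizures, so it cannot be met at 12 months. Apart from the narrow Class I-D route, one disabling seizure in the window settles the outcome as a failure. The plan has the subject write that seizure down but contains no required step to retrieve it at an early exit.

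If it is not retrieved, the subject's outcome is missing and is drawn from a model that uses no post-procedure seizure data and no exit reason. A settled outcome is replaced by a random one. In a single-arm trial judged against a fixed 43%, nothing in a comparator offsets any resulting error.

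**Working it through.** **Inputs from the documents**
- Test level (Protocol 14.2): "All statistical tests will be conducted at a two-sided alpha level of 0.05 unless otherwise stated".
- Pass rule (Protocol 14.1): "The lower bound of the 95% CI of the seizure freedom rate following the Visualase procedure must be above 43"%.
- Expected rate (Protocol 14.1): "approximately 56% of subjects who undergo the Visualase procedure will be seizure free through 12 months post procedure". Treated N = 150, stated power 89%.
- Visit windows (Protocol Table 5): 6-month visit day 150 to 210, target 180; 12-month visit day 365 to 410, target 365.

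**Assumed, because the documents do not give it:** the number of treated subjects who exit early with an undetermined outcome, and the share of them who are true failures. The 30% attrition in Protocol 14.1 falls between consent and treatment and does not supply this.

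**1. The plan's own figure.** With an exact (Clopper-Pearson) two-sided 95% interval, the smallest passing count is 77/150 = 51.3%, lower bound 43.05%; 76/150 gives 42.39% and fails. P(X ≥ 77 | n = 150, p = 0.56) = 0.891, which reproduces the stated 89%. P(X ≥ 77 | n = 150, p = 0.43) = 0.0244.

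**2. The gap.** Target to target: 365 − 180 = 185 days. Widest case: 410 − 150 = 260 days.

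**3. All k exits are uncollected failures, true rate 43%.** The expected true successes, 150 × 0.43 = 64.5, all lie among the 150 − k observed subjects. Imputation carries the observed rate p* = 64.5/(150 − k) to the exits, so the expected estimate is p*. The false-pass chance is approximated by P(X ≥ 77 | n = 150, p*), which ignores imputation variance.

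| k | p* | False-pass chance |
|---|---|---|
| 0 | 43.0% | 2.4% |
| 3 | 64.5/147 = 43.9% | 4.0% |
| 5 | 64.5/145 = 44.5% | 5.4% (about 5.5%) |
| 8 | 64.5/142 = 45.4% | 8.5% |

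A simulation (20,000 trials per scenario, 10 imputations, uninformative covariates, Rubin's rules with a t interval) gave 4.5% for 4 exits and 8.1% for 8, so 8 to 8.5% is a fair statement for k = 8.

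**4. Exits that are not all failures, same simulation.**

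| Share of exits that fail | 8 exits | 15 exits |
|---|---|---|
| 57% (the overall rate) | 2.5%, estimate 43.0% | 2.5%, estimate 43.0% |
| 75% | 4.5%, estimate 44.0% | 6.8%, estimate 45.0% |
| 100% | 8.1%, estimate 45.4% | 19.3%, estimate 47.8% |

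The inflation comes from enrichment for failures, not from early exit as such.

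**5. Does better collection alone cure it?** Take 8 exits at random with a true rate of 43%. The 142 completers give 142 × 0.43 = 61.06 expected successes, and 8 × 0.57 = 4.56 exits are failures. If half of these are captured and the other exits are imputed at the observed rate, the estimate is 61.06/(142 + 2.28) = 42.3%. If all are captured, it is 61.06/(142 + 4.56) = 41.7%. The leavers still missing are then mostly or wholly seizure free to date, yet they are imputed as if nothing were known about them. Collecting failures without changing the imputation can bias the rate downward.

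**The case against.** The other side has substantial points.

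- *Other routes exist.* Diary review at an unscheduled visit should be done if possible. Protocol 7.15.5 allows telephone follow-up with the diary sent in remotely, and 7.19 uses all data available at exit. This stands as far as it goes, but none of it is mandatory at exit. Telephone contact is a last resort for a visit that cannot be attended. Adverse event reporting (Protocol 10.2.1) leaves out seizures that have not worsened, so a recurrence of the usual type and frequency is missed.
- *Few subjects may be affected.* To count, a subject must exit early, have a first disabling seizure after the last reviewed visit, and escape all optional collection. Entry requires at least 12 qualifying seizures in the prior year, so many failures may show by the 14-day, 3-month or 6-month review. Retreated and resected subjects already count as failures (Protocol 7.17). This stands, and k may be small.
- *Footnote 11 is secondary.* An early exit need not involve an unscheduled visit. This also stands: Protocol 7.19 with SAP 7.4.1 carries the point.
- *Parts of the plan are not visible.* Section numbers are skipped in both public texts (for example SAP 7.4.2), and the exit eCRF and its instructions are not shown. No claim is made that a sensitivity analysis or an exit-form field is absent.

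A reader might infer that the error always favours the device. The documents do not support that. Imputation also scores some seizure-free leavers as failures, and when exits fail at the overall rate the two cancel. Nor do seizures necessarily go unrecorded: the diary runs to exit, so the risk is that it is not collected. A disabling seizure already on file after day 30 should settle the outcome, although the visible SAP text does not say so.

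**Conclusion.** The gap holds as avoidable missing data on the primary endpoint: no visible provision requires seizure status at an early exit, and the imputation model could not recover it.

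Upward bias is conditional on early exits being enriched for failures. That is plausible, since Protocol 7.17 lets a subject who is not Engel Class I and is refused retreatment be withdrawn, though some of those failures will already be on record. It is not demonstrated. If every exit is an uncollected failure and the true rate is 43%, the false-pass chance moves from 2.4% to about 4%, 5.5% and 8 to 8.5% for 3, 5 and 8 exits. At a 75% failure share, 8 exits give 4.5%. At the overall failure rate there is no inflation. Every exit count and failure share here is an assumption. The stated 89% power is reproduced and is not in question.

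**What to change.** 1. **Protocol 7.19 and the Study Exit eCRF.** For every treated subject, require diary return or, failing that, the subject-reported date and type of any seizure since the last review. Allow this by telephone, and place it before exit is completed, because no data are collected afterwards.
2. **Protocol Table 2 footnote 11, 7.16 and Table 4.** Require diary review at unscheduled visits after the procedure, and mark the diary forms in the unscheduled column of Table 4 so that it agrees with Table 2 and 7.16.
3. **SAP 7.4.1.** State that a documented disabling seizure from day 30 to day 365 is a failure without imputation, subject to Class I-D. Impute the remaining early exits conditional on being seizure free to their last diary date, for example from subjects who were also seizure free at that date. This keeps the outcome binary and needs no daily-level imputation. Item 3 must accompany items 1 and 2, or the added data can pull the estimate down (42.3% or 41.7% against a true 43% in the example with 8 exits).

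The cost is a few eCRF fields, protocol and SAP wording, and a little site effort at withdrawal. No new visit is needed. Some subjects will decline or be unreachable, so the gap will shrink rather than vanish.
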